**Table 1: CAPS-5 Data Collection by Visit**

CAPS Number	Visit	Description/Timing	Target Timing Post Baseline
Baseline CAPS-5 T1	V3	Baseline between Visits 2 and 4 (Preparatory Sessions), after medications have been tapered.	Not Applicable
CAPS-5 T2	V13 (2-session group) or V17 (3-session group)	Post Treatment Primary Outcome 49 to 56 days after last Experimental Session	63 to 98 days or 85 to 134 days
CAPS-5 T2.2	V15 (2-session group only)	Secondary outcome for 2-session group only 28 to 35 days after T2	85 to 134 days

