**Table 5: Treatment Period, Follow-Up, and Study Termination-Group 1 (3 Experimental Sessions)**

	Treatment Period: Group 1 (3 Experimental Sessions) ~9-15 weeks												Post-Treatment Period (~5 weeks)		
	Treatment 1				Treatment 2				Treatment 3				Primary Outcome	Outcome Site Visit	Study Termination
Visit	V5	V6	V7	V8	V9	V10	V11	V12	V13	V14	V15	V16	V17	V18	V19
Visit Description	Exp.1	Int. 1.1	Int. 1.2	Int. 1.3	Exp. 2	Int. 2.1	Int. 2.2	Int. 2.3	Exp. 3	Int. 3.1	Int. 3.2	Int. 3.3	CAPS-5 T2 Outcome: Telemedicine A	Outcome Site Visit	Study Termination
Visit Timing	Within 7 days after V3	Morn-ing after V5	~1 week (3 to 14 days) after V5	~2 weeks (10 to 21 days) after V5	~3 weeks (21 to 35 days) after V5	Morn-ing after V9	~1 week (3 to 14 days) after V9	~2 weeks (10 to 21 days) after V9	~3 weeks (21 to 35 days) after V9	Morn-ing after V13	~1 week (3 to 14 days) after V13	~2 weeks (10 to 21 days) after V13	85 to 134 days after V3; ~ 7 weeks after V13	2 days (1 to 7 days) after V17	~2 days (0 to 7 days) after V18
Past/Current Medication & Adherence	S #	S #	S #	S #	S #	S #	S #	S #	S #	S #	S #	S #		S #	S #
Drug Screen	S #				S #				S #						
Pregnancy Screen B	S #				S #				S #						
Biomarker Blood Sample													S C		
Record	S #	S #	S #	S #	S #	S #	S #	S #	S #	S #	S #	S #	S #		
All AEs D	S #	S #	S #	S #	S #	S #	S #	S #	S #	S #	S #	S #		S #	S #
Randomization E	S #														
Administer IMP	S #				S #				S #						
8-hour Exp. Session	S #				S #				S #						
BP, Pulse, Temp. F	S #				S #				S #						S G
Overnight Stay	S #				S #				S #						
90-min Integrative Session		S #	S #	S #		S #	S #	S #		S #	S #	S #			
Phone Call Follow-up H		S #				S #				S #					
Weight													#	S #	

A All visits must be scheduled to ensure that the Primary Outcome CAPS-5 T2 assessment is within the overall window provided.

B For people able to become pregnant (PAPB) only

C Blood samples will be drawn from participants at two time points (pre- and post-treatment) in order to bank samples for future assay.

D All Adverse Events (AEs) includes collecting Serious Adverse Events, Aes of Special Interest, Aes of Psychiatric Status, Aes requiring medical advice or attention, Aes that indicate withdrawal of a participant, and all other Aes

E Randomize 24 to 48 hours prior to first Experimental Session

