**Table 6: Treatment Period, Follow-Up, and Study Termination-Group 2 (2 Experimental Sessions)**

	Treatment Period: Group 2 (2 Experimental Sessions) ~6-10 weeks								Post-Treatment Period (~9 weeks)			
	Treatment 1				Treatment 2				Primary Outcome	Outcome Site Visit	Secondary Outcome	Study Termination
Visit	V5	V6	V7	V8	V9	V10	V11	V12	V13	V14	V15	V16
Visit Description	Exp. 1	Int. 1.1	Int. 1.2	Int. 1.3 G	Exp. 2	Int. 2.1	Int. 2.2	Int. 2.3	CAPS-5 T2 Outcome: Tele-medicine A	Outcome Site Visit	CAPS-5 T2.2 Outcome: Tele-medicine	Study Termination
Visit Timing	Within 7 days after V3	Morning after V5	~1 week (3 to 14 days) after V5	~2 weeks (10 to 21 days) after V5	~3 weeks (21 to 35 days) after V5	Morning after V9	~1 week (3 to 14 days) after V9	~2 weeks (10 to 21 days) after V9	63 to 98 days after V3; ~ 7 weeks after V9	2 days (1 to 7 days) after V13	85 to 134 days after V3	~2 days (1 to 7 days) post V15
Past/Current Medication & Adherence	S #	S #	S #	S #	S #	S #	S #	S #		S #	S #	S #
Drug Screen	S #				S #							
Pregnancy Screen B	S #				S #							
Biomarker Blood Sample									S C			
Record	S #	S #	S #	S #	S #	S #	S #	S #	S #			
All Aes D	S #	S #	S #	S #	S #	S #	S #	S #		S #	S #	S #
Randomization E	S #											
Administer IMP	S #				S #							
8-hour Exp.Session	S #				S #							
BP, Pulse, Temperature F	S #				S #							S G
Overnight Stay	S #				S #							
90-min IntegrativeSession		S #	S #	S #		S #	S #	S #				
Phone Call Follow-up H		S #				S #						
Weight												S #

A All visits must be scheduled to ensure that the Primary Outcome CAPS-5 T2 assessment is within the overall window provided.

B For people able to become pregnant (PAPB) only

C Blood samples will be drawn from participants at two time points (pre- and post-treatment) in order to bank samples for future assay. Post-treatment blood draw will occur within 9 days of V13.

D All Adverse Events (Aes) includes collecting Serious Adverse Events, Aes of Special Interest, Aes of Psychiatric Status, Aes requiring medical advice or attention, Aes that indicate withdrawal of a participant, and all other Aes

E Randomize 24 to 48 hours prior to first Experimental Session

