## 7.4 Post-treatment Period and Study Termination

### 7.4.1 Post-treatment Period

After the last Integrative Session, participants will enter follow-up for approximately 4 weeks with no protocol required visits until the Outcome CAPS-5 T2 assessment. This assessment will also include the SDS and the DSP-I. Participants will have access to therapy pairs for support if needed, and additional visits via phone, telemedicine, or in person can be scheduled if requested. Participants will continue to comply with protocol requirements for concomitant medications until after Study Termination.

Participants will be scheduled for an in-person visit within 1 to 7 days after the CAPS-5 T2, where qualified site staff will arrange the post-treatment blood draw, administer the MAPS-Adapted C-SSRS (Since Last Visit), and actively support participants in the completion of the self-reported outcome measures.

- WHOQOL-BREF
- AAQ-II
- SCS
- BPAQ-SF
- PCL-5
- MIES
- BDI-II
- CPGS
- PTGI
- UFEC
- AUDIT
- DUDIT

Participants in the two Experimental Session group will have a second outcome evaluation (T2.2, Visit 15) timed to be concurrent with those who completed three Experimental Sessions, approximately 4 weeks after their first post-treatment assessment at T2 (Visit 13). A blinded IR from the IR Pool will conduct the assessments via telemedicine. These assessments may be recorded to establish inter-rater reliability. Participants will be instructed to withhold from sharing with the IRs their progress in the study including how many visits or Experimental Sessions they have had.

Participants who have withdrawn from treatment will also complete a final CAPS-5 assessment immediately upon withdrawal. The IR will also administer the DSP-I and the SDS.

Following post treatment assessment, participants will engage in post treatment planning with the treatment team and are no longer required to comply with requirements related to concomitant medication or other forms of therapy.

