CAPS Number	Visit	Description/Timing	Target Timing Post Baseline
Baseline CAPS-5 T1	Screening	Baseline 2-9 days after initial eligibility met	Not Applicable
CAPS-5 T2	V12 (2-session group) or V16 (3-session group)	Post Treatment Primary Outcome 28 to 35 days after last Experimental Session	~12 wk (± 7 days) or ~16 wk (± 7 days)
CAPS-5 T2.2	V13 (2-session group only)	Secondary outcome for 2-session group only 28 to 35 days weeks after T2	~16 wk (± 7 days)

Dose Selection

This study will compare the effects of two versus three open-label manualized Experimental Sessions of therapy assisted by set doses of MDMA HCl (referred to as MDMA throughout) as described in the table below, along with associated non-drug preparatory and integrative therapy. Similar MDMA doses to those proposed in this study have been safely used in previous Phase 2 and 3 studies sponsored by MAPS.

Table 2: Dose Regimen of MDMA

Experimental Session	Initial Dose	Supplemental Dose*	Min-Max Cumulative Dose
1	120 mg	40 mg	120 mg to 160 mg
2	120 mg	40 mg	120 mg to 160 mg
3	120 mg	40 mg	120 mg to 160 mg
Total Cumulative Dose: 2 Session Group		240 mg to 320 mg	
Total Cumulative Dose: 3 Session Group		360 mg to 480 mg	

* Unless initial dose is not tolerated or refused by participant

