7.8.2 Analysis of Adverse Events

The primary measure of safety will be the reporting of unsolicited AEs. All AEs collected from Enrollment to Termination will be categorized as follows:

- Pretreatment AEs are defined as AEs that occur during the Preparatory Period prior to the first dose in the first Experimental Session
- Treatment Emergent AEs are defined as AEs that occur during the Treatment Period from the first Experimental Session to final study visit
- AEs that occur one and two days after MDMA administration
- AESIs are defined as AEs specified in the protocol related to cardiac function, serious suicidal ideation/behavior, and abuse liability
- Follow-up Period AEs are defined as AEs that occur during the Follow-up Period after the last Integrative Session through Termination
- AEs leading to discontinuation of IMP
- SAEs

Verbatim terms on case report forms will be mapped to preferred terms (PT) and system organ class (SOC) using the Medical Dictionary for Regulatory Activities (MedDRA) Version 24.0

Frequency and incidence of AEs will be displayed by PT, sorted by SOC, severity, and seriousness. AEs will be analyzed and presented as follows:

- If a participant has more than one AE mapped to the same PT, that AE will be reported once using the highest severity
- Relationship as determined by the Clinical Investigator
- AEs that occur on day of Experimental Sessions and two days after IMP administration will be presented separately.

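### Follow-up Period adverse events are counted over about 65 days in the 2-session group and 39 in the 3-session group, with no common cut-off or person-time rate (SAP 7.8.2)

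*SAP*

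**What the plan says.** SAP 7.8.2 sorts adverse events (AEs) into categories, one of which is: "Follow-up Period AEs are defined as AEs that occur during the Follow-up Period after the last Integrative Session through Termination". The wording is the same for both groups. The section displays frequency and incidence by preferred term, counting each term once per participant at its highest severity. SAP 7.8 gives the AE summaries overall and by treatment received. Neither document plans a person-time rate, a common cut-off or a caveat for this category.

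The Protocol sets the length of the window:

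- Table 5 (3 sessions) heads its last block "Post-Treatment Period (~5 weeks"; Table 6 (2 sessions) heads its own "Post-Treatment Period (~9 weeks".
- Protocol 7.4.1 starts the period at the same point for everyone: "After the last Integrative Session, participants will enter follow-up for approximately 4 weeks", up to the T2 assessment.
- Only the 2-session group then has T2.2, 28 to 35 days after T2 (Protocol Table 1), and its Termination visit follows T2.2.
- Protocol 10.1 collects AEs through Study Termination. After treatment this happens at V14, V15 and V16 in the 2-session group (Table 6), and at V18 and V19 in the 3-session group (Table 5).

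**The concern.** Crude incidence depends on how long participants are watched. If one group is observed for about four weeks longer in a category, more of its participants will have an event there, even when the underlying rates are the same. A reader of side-by-side columns could then conclude that two sessions leave participants with more late AEs than three.

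This deserves attention because SAP Section 1 moves the focus of the analysis to safety only, and SAP 7.8.2 names unsolicited AEs as the primary measure of safety. With about 20 participants in all, a difference of one or two people is enough to colour a table.

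**Working it through.** **Inputs (days).**

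- Last Integrative Session after the last Experimental Session: "2 weeks (10 to 21 days) after V13" (3-session, Table 5) and "2 weeks (10 to 21 days) after V9" (2-session, Table 6), taken as 14 nominal.
- T2, Protocol Table 1: "Post Treatment Primary Outcome 49 to 56 days after last Experimental Session". Nominal 49, since Tables 5 and 6 say about 7 weeks.
- T2.2, 2-session only: 28 to 35 after T2; nominal 28.
- 3-session: outcome site visit V18 is 1 to 7 after T2 (nominal 2); Termination V19 is 0 to 7 after V18 (nominal 2).
- 2-session: Termination V16 is 1 to 7 after T2.2 (nominal 2).

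**Step 1. Reproduce the Protocol's period lengths** (last Integrative Session to Termination).

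| Group | Nominal | Minimum | Maximum |
|---|---|---|---|
| 3-session | (49−14)+2+2 = 39 (5.6 weeks) | (49−21)+1+0 = 29 | (56−10)+7+7 = 60 |
| 2-session | (49−14)+28+2 = 65 (9.3 weeks) | (49−21)+28+1 = 57 | (56−10)+35+7 = 88 |

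Using the Protocol's text of about 4 weeks, then 4 more, gives 28+2+2 = 32 days (4.6 weeks) and 28+28+2 = 58 days (8.3 weeks). Both routes agree with the table headings of about 5 and 9 weeks. The nominal ratio of time at risk is 65/39 = 1.67, and the permitted ranges overlap only from 57 to 60 days.

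**Step 2. Effect on crude incidence.** The documents give no AE rate, so the 3-session incidence p3 is an assumption and is shown over a range. With the same constant rate in both groups, p2 = 1 − (1 − p3)^(65/39). The last column assumes 10 per group, from 1:1 allocation of about 20.

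| p3 | p2 | Difference (points) | Expected participants, 3- v 2-session |
|---|---|---|---|
| 5% | 8.2% | 3.2 | 0.5 v 0.8 |
| 10% | 16.1% | 6.1 | 1.0 v 1.6 |
| 20% | 31.1% | 11.1 | 2.0 v 3.1 |
| 30% | 44.8% | 14.8 | 3.0 v 4.5 |

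**Step 3. Declining rate.** Suppose the rate halves every h weeks from the start of follow-up. On the rounded 5- and 9-week periods, p2 = 1 − (1 − p3)^(C9/C5), with Ct = 1 − 2^(−t/h). For p3 = 20% and h = 1, 2, 4, 8 weeks (assumed), p2 = 20.5%, 22.8%, 26.2%, 29.1%. The direction is the same and the size smaller.

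**Step 4. Overall treatment-emergent window** (first Experimental Session to final visit, session gap g): 3-session 2g+49+2+2; 2-session g+49+28+2. For g = 21, 28, 35 this gives 95 v 100, 109 v 107, 123 v 114 days, which is close to balanced.

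**Step 5. Conflict on T2 timing.** SAP Table 1 has "Post Treatment Primary Outcome 28 to 35 days after last Experimental Session". With that timing and the Protocol's other intervals, the nominal windows are (28−14)+2+2 = 18 and (28−14)+28+2 = 44 days, a ratio of 2.4. The imbalance remains under either document.

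**The case against.** The strongest reply is that no such comparison is planned. SAP 7.8.2 only says that AEs will be categorized. The events it promises to present separately are those on session days and the two days after, and the only AE comparison SAP 7.8 names is for events during Experimental Sessions. This stands in part: a by-group Follow-up table is a fair reading of SAP 7.8 with 7.8.2, but it is not spelled out. A reader might infer that the trial's safety comparison as a whole is biased by design. The documents do not support that. T2.2 is timed to coincide with the 3-session T2 (Protocol 7.4.1), every Follow-up AE also falls within the treatment-emergent total, and those windows nearly match (Step 4). The longer follow-up after two sessions is the counterpart of a shorter treatment period.

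The second reply concerns size. A reader who takes the rounded 5 and 9 weeks with incidences of 20% and 30% gets 33% and 47%, an artefact of 13 to 17 points. Those incidences appear nowhere in the documents. The nominal days give 11 to 15 points, lower incidences give 3 to 6, and a constant rate is itself doubtful: Protocol 9.2.4.1 describes common expected AEs as transient and typically diminishing over 72 hours after dosing, while follow-up begins at least 10 days after dosing. A constant rate suits background events better than drug effects.

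Third, the tables are descriptive, so no test or conclusion depends on them. That is correct, and it limits the weight of the point. It does not remove it, because columns by treatment received invite comparison and nothing tells the reader that the windows differ.

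**Conclusion.** The point holds in a limited form. The Follow-up category has about 1.7 times as much time at risk in the 2-session group, and its crude incidence is inflated there as long as events keep occurring in the extra weeks. Under equal constant rates and the nominal windows, the inflation is 3 to 15 percentage points for assumed 3-session incidences of 5% to 30%, or 0.3 to 1.5 participants with 10 per group. It is smaller if rates decline. It affects one descriptive category only, not the treatment-emergent totals and not any formal test.

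The windows apply to participants treated as scheduled. Grouping by treatment received, and early terminations, will make individual follow-up vary further.

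**What to change.** In SAP 7.8.2, state that Follow-up Period AEs will be shown by group with events per participant-week, using each participant's actual days from the last Integrative Session attended to Termination, and with median follow-up days per group. Say whether repeat events of one term count in the numerator. This handles early terminations. It equalises the groups only if the rate is roughly constant: with a 2-week half-life in Step 3, cumulative events rise 1.16-fold over 1.8 times the person-time, so the 2-session rate would look about 0.65 times the other. The median days should therefore be printed alongside.

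Alternatively, end the by-group table at the T2 outcome site visit (Protocol V14 or V18), or at Termination if earlier, and list all later AEs separately in both groups, including 3-session events between V18 and V19. For participants who reach that visit, the window is then (49−21)+1 = 29 to (56−10)+7 = 53 days in either group, nominally 37, and no constant-rate assumption is needed.

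Before a visit-based cut is programmed, SAP Table 1 (T2 at V12 or V16, 28 to 35 days after the last session) must be reconciled with Protocol Table 1 (V13 or V17, 49 to 56 days).

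Either option is a cheap improvement: a sentence in the SAP and a small programming change before database lock, at the price of one extra column or listing. No new data are needed.

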7.8.3 Concomitant Medications

Frequency and incidence of concomitant medications will be displayed by generic name, sorted by class, and summarized by treatment group.

7.8.4 Analysis of Suicidal Ideation and Behavior

A positive response for suicidal ideation is counted when a participant answers “yes” to any one of the five suicidal ideation questions (Categories 1-5) on the C-SSRS (i.e., a score >0 for suicidal ideation). Serious suicidal ideation is a suicidal ideation score of 4 or 5. A positive response for suicidal behavior occurs when a participant answers “yes” to any one of the five suicidal behavior questions (Categories 6-10) on the C-SSRS. The number and percent of positive responses of Positive Ideation, Serious Ideation, and Positive Behavior will be tabulated by treatment group and time period (lifetime, screening, baseline, each Experimental Session (pre- and post-IMP), Integrative Sessions, and endpoints). Frequency and incidence of positive or serious ideation and suicidal behavior will be presented using descriptive statistics in tabular format. A Shift table of changes in suicide ideation since baseline will be presented.

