## 6.3 Screening Measures and Reliability

### 6.3.1 C-SSRS (Columbia Suicide Severity Rating Scale); MAPS-Adapted

The C-SSRS is a clinician-administered measure of suicidal behavior devised to detect potential suicidal thoughts or behaviors during a clinical trial [73]. It consists of a “Baseline/Screening” version and a “Since Last Visit” version that assess suicidal ideation, ideation intensity, and behavior. The C-SSRS consists of a series of questions and can be administered during a face-to-face interview or over the telephone. The Baseline/Screening version assesses the experience of the participant with suicidal ideation and behavior over their lifetime and within 6 months prior to entry into the trial and will be completed for all potential participants at screening to determine eligibility. All subsequent administrations will utilize the Since Last Visit version to assure that the participant continues to qualify for the trial. Participants who are discontinuing medications to participate in the study will complete the C-SSRS before and after medication washout. The C-SSRS Intensity scale for Lifetime obtained a Cronbach’s alpha of 0.93 and 0.94 for the Since Last Visit form, and Last Visit C-SSRS severity scores were positively correlated with the BDI “suicide thoughts” item [74]. This study will utilize the MAPS-adapted versions of the Baseline/Screening and Since Last Visit C-SSRS measures. The MAPS Adapted C-SSRS was developed utilizing [name] Columbia Suicide Severity Scale. The MAPS Adapted C-SSRS maintains the content and flow of the standard C-SSRS. The scale was adapted to modify formatting and add additional administrative guidance to reduce rater and data entry errors. The MAPS Adapted C-SSRS has been approved by [name] for use in MAPS Research.

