**Table 7: Time and Events-Study Measures-Group 1 (3 Experimental Sessions)**

	Screening				Baseline & Enrollment Confirmation		Treatment 1			Treatment 2			Treatment 3			Post-Treatment Follow-Up& Study Termination		
	Visit #	Site A	IR Screening	V0	V3	V4	V5	V6 & 7	V8	V9	V10 & 11	V12	V13	V14 & 15	V16	V17	V18	V19
Visit Description	~Time to Complete Measure (minutes)	Site Visit	Tele-medicine	Site visit	Baseline CAPS-5 T1	Prep. 3 & Enrollment Confirmation	Exp. 1	Int. 1.1 & 1.2	Int. 1.3	Exp. 2	Int. 2.1 & 2.2	Int. 2.3	Exp. 3	Int. 3.1 & 3.2	Int. 33	CAPS-5 T2 Outcome: Telemedicine	Outcome Site Visit	Study Termination
CAPS-5	90 (Baseline) 60 (all others)				✓											S #		
SDS	5				✓											✓		
DSP-I	15				✓											✓		
MINI	15		✓															
SCID-5-PD	60		✓															
SCID-5-SPQ	20	✓																
WHOQOL-BREF	10					✓											✓	
AAQ-II	3					✓											✓	
C-SSRS B	10	✓	✓	✓#	#	S	S C	S #	S #	S C	S #	S #	S C	S #	S #	#	S #	S #
SCS	6					✓											✓	
DDIS D	5		✓															
BPAQ-SF	12					✓												✓
DRRI-II E	11			✓														
LEC-5	5	✓																
PCL-5	8	✓					S F			S F			S F				✓	
MIES	4					✓											✓	
ACE	4			✓														
BDI-II	10 (Baseline) 5 (all others)						✓ G			✓ G			✓ G				✓	
CPGS	5						✓										✓	
PTGI	8						✓										✓	
OSU-TBI	5			✓														
UFEC	3			✓													✓	
AUDIT	3	✓															✓	
DUDIT	3	✓															✓	
~Total Time of Completing Measures (minutes)	49	90	23	110	76	23	10	10	23	10	10	23	10	10	10	80	80	80

A Ensure that LEC-5 and SCID-5-SPQ results are sent to the Independent Rater who will be conducting the SCID-5-PD

B First C-SSRS is a Baseline/Screening assessment, other assessments are Since Last Visit. Additional C-SSRS measures may be conducted as clinically indicated. The site will utilize the MAPS-adapted C-SSRS.

C Conducted pre- and post-IMP administration, and at phone calls every other day for 14 days starting 2 days after Experimental Session

D The relevant questions (117-130) from the DDIS will be asked by the Independent Rater during the SCID-5-PD assessment. The entire measure will never be administered.

E Only scales D (combat experiences) and E (post-battle experiences) of the DRRI-II will be administered.

F PCL-5 conducted pre-IMP administration.

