### **7.3.2 Telephone Contact After Experimental Sessions**

The goal of the telephone contact is to assess health changes, ensure participant safety, and offer support. A member of the therapy pair will follow-up with the participant by telephone on every other day for 14 days after each Experimental Session (starting 2 days post-Experimental session). Each call will last on average five to 15 minutes but could be longer to address participant concerns and to adequately assess wellbeing. Additional telephone contact can be initiated at the request of the therapy pair or participant.

At each telephone contact, the member of the therapy pair will:

- Inquire about any possible changes in health, assess the participant's mental health and the status of any previously recorded Aes, and record Aes as described in [Section 10.0 Safety](#).
- Inquire about concomitant medication use and adherence.
- Offer support in accordance with the Treatment Manual.
- Administer the Since Last Visit C-SSRS.

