#### *Treatment 1*

- Integrative Session 1.1 (Visit 6): morning after Experimental Session 1 (Visit 5).
- Integrative Session 1.2 (Visit 7): ~1 week (3 to 14 days) after Experimental Session 1 (Visit 5).
- Integrative Session 1.3 (Visit 8): ~2 weeks (10 to 21 days) after Experimental Session 1 (Visit 5). This visit serves two purposes: to continue integration and to prepare for the next Experimental Session.

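### SAP 7.8.4 states no row for the C-SSRS forms taken by telephone in the two weeks after each Experimental Session, so its by-period suicidality table can understate ideation

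*SAP*

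**What the plan says.** SAP 7.8.4 defines three C-SSRS outcomes: positive ideation (any score above 0), serious ideation (a score of 4 or 5) and positive behavior. It tabulates each by treatment group and "time period (lifetime, screening, baseline, each Experimental Session (pre- and post-IMP), Integrative Sessions, and endpoints". Two further outputs follow in the same section: a general statement that frequency and incidence will be shown in tables, and a shift table of ideation since baseline. Neither says which post-baseline forms it uses.

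The protocol collects more C-SSRS forms than this list names. Footnote C of Tables 7 and 8, attached to the Experimental Session cells, reads "Conducted pre- and post-IMP administration, and at phone calls every other day for 14 days starting 2 days after Experimental Session". Protocol 7.3.2 sets the calls "every other day for 14 days after each Experimental Session (starting 2 days post-Experimental session") and lists among the tasks at each call: "Administer the Since Last Visit C-SSRS". On the version of the form, protocol 6.3.1 says, after the Screening form, "All subsequent administrations will utilize the Since Last Visit version".

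**The concern.** The SAP keeps the footnote's pre-/post-IMP wording and leaves out its telephone part. No other SAP section assigns the telephone forms to a period, and no row gives incidence at any time after first dose. A programmer who follows the list literally has no row for them.

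This carries more weight because the SAP is now a safety-only plan (SAP 1.0). Safety objective 10 (SAP 2.3) is the incidence of serious ideation and positive behavior on the C-SSRS. The forms without a row fall in the two weeks after each dose, where a drug- or session-related change would be looked for. A later form need not recover what a call recorded, because each later form asks only about the time since the last visit.

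**Working it through.** The plan states no figure to reproduce, so the check counts forms per treatment cycle and compares them with the SAP list.

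**Inputs**
- Calls start on day 2 and run on alternate days for 14 days (protocol 7.3.2).
- C-SSRS before and after IMP at each Experimental Session (Tables 7 and 8, footnote C).
- C-SSRS at three Integrative Sessions per cycle (Tables 7 and 8). Protocol 7.3.3 puts the first on day 1, the second at about day 7 (window: days 3 to 14) and the third at about day 14 (window: days 10 to 21), counted from the dose. Treatments 2 and 3 use the same windows.

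**1. Telephone forms.** Days 2, 4, 6, 8, 10, 12 and 14: (14 − 2)/2 + 1 = 7 per Experimental Session. Per participant this is 7 × 2 = 14 in the 2-session group and 7 × 3 = 21 in the 3-session group.

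**2. Forms with a stated row.** 1 pre-IMP + 1 post-IMP + 3 Integrative = 5 per cycle, of which 4 are post-dose.

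**3. Share with no stated row.** All forms in a cycle: 7/(7 + 5) = 58%. Post-dose forms only: 7/(7 + 4) = 64%.

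**4. Days covered only by a call.** Assume each form looks back to the previous C-SSRS, with Integrative Sessions on target days 1, 7 and 14. Intervals that end in a call are days 1-2, 2-4, 4-6, 7-8, 8-10 and 10-12: 1 + 2 + 2 + 1 + 2 + 2 = 10 days. Days 12-14 go to whichever form is taken first on day 14. So 10 or 12 of the 14 days rest on a telephone form alone. Over all allowed Integrative windows the range is 9 to 13 days.

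**5. Effect of the recall rule.** Take ideation on day 3, reported on the day 4 call. If recall runs from the last C-SSRS, the day 7 Integrative form looks back only to the day 6 call and does not pick it up. If recall runs from the last in-person visit, the day 7 form looks back to day 1 and does pick it up. The protocol does not say which rule applies.

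**6. Scale in the trial.** Assume the approximately 20 participants at termination split 10/10 and complete every session and call. Sessions: 10 × 2 + 10 × 3 = 50. Telephone forms: 50 × 7 = 350. Post-dose forms with a stated row: 50 × 4 = 200. In a group of 10, one participant positive only by telephone changes incidence by 1/10, or 10 percentage points. How many such participants there are is unknown.

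**The case against.** Five points can be made on the other side.

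- **The forms may fit a listed period.** Footnote C sits in the Experimental Session columns, which suggests post-IMP. Tables 5 and 6 mark the calls in the columns of the first Integrative Session of each cycle, which suggests Integrative Sessions. Both placements are reasonable, but the SAP adopts neither, and two programmers could produce different tables from the same data.
- **Other outputs are not restricted to the list.** The general incidence statements in SAP 7.8 and 7.8.4 and the shift table do not exclude telephone forms. This stands. A reader might infer that telephone-only ideation appears nowhere in the report, and the documents do not support that. Equally, these sentences name no forms, no any-time row and no worst-value rule, so they do not ensure inclusion.
- **Recall may recover the reports.** The protocol calls these calls contacts, and the form asks about the time since the last visit. If only in-person visits count, Integrative forms cover the call intervals again. The documents leave this open.
- **The more serious events have a second route.** Ideation scores of 4 to 5 and suicide attempts are AESIs (protocol 10.1.1), protocol 9.1.2 routes positive suicidal behavior to AESI capture, and SAP 7.8.2 counts both as AESIs. This stands, although safety objective 5 in SAP 2.3 describes AESIs as cardiac and abuse liability only. Scores of 1 to 3 have no definite second route: they become AESIs only if judged serious or severe. Objective 10 does not name those scores, but SAP 7.8.4 itself undertakes to count any score above 0.
- **Listed forms fall in the same two weeks.** Post-IMP, day 1, about day 7 and about day 14 are all tabulated, so only part of the window is affected.

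**Conclusion.** The omission is real and should be corrected before the analysis is run. The enumerated list in SAP 7.8.4 gives no stated row to 7 of 12 C-SSRS forms per cycle (7 of 11 post-dose), and no row gives incidence at any time after first dose. Ideation or behavior reported only on a call can be missing from the by-period table, and incidence there can be understated, chiefly for ideation scores of 1 to 3.

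Two stronger readings do not follow. The first is that incidence is biased downward: that depends on the recall rule and on how the forms are mapped, neither of which is stated. The second is that 58% of the suicidality signal is lost: 58% counts forms, while incidence depends on participants who are positive only by telephone, and that number is unknown.

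The form counts assume that all scheduled calls and visits take place. The day counts also assume recall from the previous C-SSRS.

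**What to change.** In SAP 7.8.4:

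- Add a period for post-session telephone contacts, Days 2-14, for each Experimental Session.
- Add a row for any time from first dose to Study Termination, using each participant's worst value over all C-SSRS forms, including those taken by telephone.
- Use the same worst post-dose value in the shift table.

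A sentence mapping the telephone forms to a period would alone remove the ambiguity about where they go. The any-time row goes further: it gives incidence per participant, counts each participant once, and takes in every post-dose form whichever recall rule sites used.

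The cost is two kinds of table row and minor programming. The protocol already requires these data, and no study procedure changes.
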